6.2.1.3 Dosage Adjustments, Delays, Rules for Withholding or Restarting, Permanent Discontinuation

Talimogene laherparepvec treatment should be continued based on the potential benefit/risk assessment of the subject.

Dose reduction within a cohort for an individual subject who experience adverse events is not allowed. If in the course of administration of talimogene laherparepvec the subject cannot tolerate the full dose due to an injection-related adverse event, the total volume given should be recorded, and the reason for intolerance should be documented as an adverse event.

If a subject experiences any of the following treatment-related toxicities, administration should be delayed until the toxicity has resolved to at least CTCAE grade 1 or baseline:

- grade 2 or greater immune-mediated adverse events, with the exception of vitiligo
- grade 2 or greater allergic reactions
- any other grade 3 or greater hematologic or non-hematologic toxicity

If the subject requires corticosteroid dosing greater than that required for maintenance physiologic replacement therapy, talimogene laherparepvec dosing should be withheld.

If a subject demonstrates evidence of new or worsening CNS metastases, all study treatments should be withheld. Resumption of talimogene laherparepvec dosing should be left to the discretion of the investigator and discussed with the Amgen medical monitor.

If talimogene laherparepvec treatment is delayed by > 1 week, that dose will be deemed to have been missed and the subject will proceed to the next scheduled treatment visit.

If talimogene laherparepvec dosing is delayed by more than 6 weeks from the date of the planned dose due to the occurrence of an adverse event that is considered related to talimogene laherparepvec, the subject must be permanently withdrawn from talimogene laherparepvec treatment. If talimogene laherparepvec dosing is delayed by more than 6 weeks from the date of the planned dose for reasons other than treatment-related toxicity, the case must be reviewed by the Amgen medical monitor in conjunction with the investigator to determine if the subject can resume talimogene laherparepvec therapy. Reason for dose change of talimogene laherparepvec is to be recorded on CRF.

Talimogene laherparepvec will be permanently discontinued for subjects meeting any of the following criteria:

- Subject developed DLT during the DLT evaluation period.
- The subject, for any reason, requires treatment with another anticancer therapeutic agent for the study disease (other than the exceptions noted in [Section 6.4](#)). In this case, discontinuation from the study treatment occurs immediately upon introduction of the new agent.
- Confirmed PD occurs as defined per modified irRC-RECIST or clinical progression per the investigator.
- A grade 2 or greater immune-mediated adverse event (with the exception of vitiligo) or allergic reactions attributed to talimogene laherparepvec that would require a dose delay of greater than 6 weeks from the date of the planned dose.
 - NOTE: immune-mediated glomerulonephritis, vasculitis, and pneumonitis and exacerbation of psoriasis have been observed in subjects receiving talimogene laherparepvec in clinical trials. Most of these subjects had a history of other autoimmune disease and/or prior treatment with agents that offered plausible alternative etiologies; however, immune-mediated adverse events can potentially involve any organ system.
- Any other talimogene laherparepvec-related non-hematologic or hematologic toxicities grade 3 or greater that, in the opinion of the investigator, would require a dose delay of greater than 6 weeks from the date of the planned dose.
- The subject develops clinical evidence of any systemic herpetic infection (such as encephalitis or disseminated infection).

Approved

- An FCBP subject becomes pregnant or fails to use acceptable method(s) of effective contraception.
- A female subject breastfeeds while on study treatment.
- Concurrent medical illness that, in the judgment of the investigator, would make continued treatment with talimogene laherparepvec dangerous for the subject.
- Subject or legally acceptable representative withdraws consent/assent or wishes to stop the study treatment.

For additional information related to special warnings and precautions for the use of talimogene laherparepvec please refer to the latest version of the [talimogene laherparepvec Investigator's Brochure](#).

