6.4.3 Criteria for Rechallenge of Amgen Investigational Product After Potential Hepatotoxicity

The decision to rechallenge the subject should be discussed and agreed upon unanimously by the subject or legally acceptable representative, investigator, and Amgen medical monitor.

If signs or symptoms recur with rechallenge, then Amgen investigational product, as appropriate should be permanently discontinued. Subjects who clearly meet the criteria for permanent discontinuation (as described in [Section 6.4.1](#)) should never be rechallenged without consulting with the Amgen medical monitor.

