6.6 Other Treatment Procedures

Local radiation treatment to the site of bone and other metastasis will be permitted for palliative pain management at any time during the study. If a subject undergoes local radiation, the investigator or designee should notify the sponsor's medical monitor as soon as possible.

If a subject demonstrates evidence of new or worsening CNS metastases, all study treatments should be withheld and the investigator or designee should notify the sponsor's medical monitor as soon as possible. Subjects may be allowed to remain on study after discussion between the sponsor's medical monitor and the investigator to determine the appropriateness of treatment resumption provided CNS lesions are adequately treated and corticosteroid dose does not exceed levels typically required for maintenance physiologic replacement. Re-exposure to talimogene laherparepvec may occur only if the investigator and sponsor agree that the subject safety will not be compromised.

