7.3.13 Radiographic Assessment

[figure not shown]
Radiologic imaging of all sites of disease must be performed (including imaging of the brain when clinically indicated). The choice of imaging modality(ies) for tumor assessment should be tailored according to what is appropriate for the tumor type being assessed (eg, computed tomography [CT] or MRI of the primary tumor and CT of the chest may be sufficient for subjects with primary osteosarcoma whereas CT/MRI of the primary tumor as well as metastatic site[s], bone scan, and metaiodobenzylguanidine scan may be appropriate in subjects with neuroblastoma). All subsequent tumor assessments should include at least the same imaging modality(ies) and equipment as in baseline. Assessment of tumor response will be performed according to modified irRC-RECIST ([Appendix D](#)). Response (CR or partial response [PR]) or PD is to be confirmed by a second consecutive clinical and radiographic assessment no less than 4 weeks from the date of the first documented response or PD.

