^b Disappearance of all non-lymph node lesions and all lymph nodes < 10 mm in short axis would also be CR even if lymph node measurements prevent 100% tumor burden reduction.

^c No non-target lesions identified at baseline.

^d Assuming response (CR or PR) or progression are confirmed by a second, consecutive assessment at least 4 weeks (28 days) apart.

^e In addition to relative increase of ≥ 20%, the tumor burden must also demonstrate an absolute increase of ≥ 5 mm from nadir for PD.

^f No target lesions identified at baseline. When a subject has only nonmeasurable disease (ie, no target lesions identified at baseline) the response will be (UE) unevaluable.

^g If one or more target/new measurable lesions are unevaluable or not measured but the sum of all evaluable target/new lesions measured show a ≥ 20% and at least 5 mm absolute increase relative to nadir, then the visit overall Target Response will be PD.

Determination of best overall response is based on changes in total tumor burden from the baseline (nadir, for PD) tumor assessment, regardless of any initial increase in baseline lesions or the appearance of new lesions.

Subjects are considered to have partial response (PR) or stable disease (SD) even if new lesions were present, as long as they met the respective thresholds of response as described in [Table 7](#).

A best overall response of SD requires a visit response of SD or better no earlier than 49 days after the date of enrollment; otherwise the overall response will be UE.

Approved

Confirmation of Response (CR or PR):

To be assigned a status of CR or PR changes in tumor measurements must be confirmed by consecutive repeat assessments performed no less than 4 weeks (28 days) after the criteria for response are first met.

In some circumstances it may be difficult to distinguish residual disease from normal tissue. When the evaluation of CR depends on this determination, it is recommended that the residual lesion be investigated (ie, biopsy) to confirm the CR status.

Confirmation of Disease Progression:

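### Protocol 6.2.1.3 and 6.6 set different rules for restarting treatment after new or worsening CNS metastases

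*Protocol*

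**What the plan says.** Protocol 6.2.1.3, on dose delays and restarting, states the trigger and the action: "If a subject demonstrates evidence of new or worsening CNS metastases, all study treatments should be withheld". On restarting, it continues: "Resumption of talimogene laherparepvec dosing should be left to the discretion of the investigator and discussed with the Amgen medical monitor". It sets no condition on the state of the CNS lesions. A separate sentence in the same section deals with steroids: "If the subject requires corticosteroid dosing greater than that required for maintenance physiologic replacement therapy, talimogene laherparepvec dosing should be withheld".

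Protocol 6.6, on other treatment procedures, has the same trigger and the same withholding action, and adds that the sponsor's medical monitor must be told promptly. The monitor and the investigator then discuss whether resumption is appropriate, "provided CNS lesions are adequately treated and corticosteroid dose does not exceed levels typically required for maintenance physiologic replacement". It closes with: "Re-exposure to talimogene laherparepvec may occur only if the investigator and sponsor agree that the subject safety will not be compromised".

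On CNS metastases, neither section refers to the other or says which one takes precedence.

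**The concern.** Discussing a restart with the medical monitor is not the same as needing the sponsor's agreement, and having no lesion condition is not the same as requiring treated lesions. Two sites could handle the same subject differently, and each could point to the protocol in support.

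The looser wording is also the one a site is more likely to find first, because the title of 6.2.1.3 names withholding and restarting while 6.6 has a general title.

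What is at stake is whether a paediatric or young adult subject with untreated CNS metastases can be re-dosed with a virus derived from HSV-1. The protocol treats CNS risk seriously elsewhere. Exclusion criterion 233 bars clinically active brain metastases and admits treated ones only with radiographic improvement and no interim progression. Section 6.2.1.2 terminates the study if a DLT is a serious herpetic event, such as encephalitis, shown to be caused by the product. Read alone, 6.2.1.3 could allow re-dosing of a subject whose CNS disease would have barred entry.

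**Working it through.** The plan gives no figure to reproduce here, so the check is a comparison of texts.

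**Step 1: the two rules side by side**

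| Element | Section 6.2.1.3 | Section 6.6 |
|---|---|---|
| Trigger | New or worsening CNS metastases | Same |
| Immediate action | Withhold all study treatment | Same, and notify the medical monitor |
| Who decides on restart | Investigator, after discussion with the monitor | Investigator and sponsor must agree |
| CNS lesions treated | Not stated | Required |
| Steroid dose within physiologic replacement | Required, in a separate sentence | Required |

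Conditions on restart in 6.6: 3. Also found in 6.2.1.3: 1 (steroids). Missing from 6.2.1.3: 3 − 1 = 2.

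**Step 2: do other stopping rules cover these subjects anyway?**

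Section 6.2.1.3 permanently stops treatment for confirmed PD, for clinical progression as judged by the investigator, and when another anticancer agent is needed. These cover some subjects with CNS metastases, but not all:

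- Appendix D states: "Subjects are considered to have partial response (PR) or stable disease (SD) even if new lesions were present", provided the tumour-burden thresholds are met. In Table 7, a burden change between a decrease of less than 30% and an increase of less than 20% is SD whatever new non-measurable lesions exist, and even with unequivocal non-target progression. A small new CNS lesion therefore need not produce PD.
- Where the threshold for PD is reached, Section 7.3.13 says: "PD is to be confirmed by a second consecutive clinical and radiographic assessment no less than 4 weeks". Appendix D waives confirmation for rapid clinical deterioration or for symptomatic disease needing prompt alternative systemic therapy. Otherwise the subject is not yet a confirmed progressor.
- Clinical progression is the investigator's own judgement, so it adds no independent check on an investigator who wants to restart.

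In these situations the restart rule is what decides.

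**Step 3: the length of the window**

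The minimum confirmation interval for PD is 28 days and maintenance dosing is every 14 days: 28 / 14 = 2 scheduled doses. This is illustrative only. Both sections withhold treatment at the trigger, so no dose is given by default; the 2 doses are those that a restart decision in that interval could release. The figure applies to the 14-day phase, as the first dosing interval is 21 days.

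**The case against.** The strongest reply is that the two rules add together and do not contradict each other. Section 6.6 is in force and restrictive, 6.2.1.3 does not waive it, and a site must follow the whole protocol. On that reading the stricter conditions always bind, and a restart without sponsor agreement is a deviation. It is true that a site following 6.6 meets both sections. But leaving a decision to the investigator's discretion names a different decision-maker from requiring joint agreement, and a reader of 6.2.1.3 has no signal that further conditions exist.

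Three further points have weight:

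- **The medical monitor is involved under both sections.** A restart with untreated lesions would normally mean that both the investigator and the monitor had overlooked 6.6. This lowers the practical risk, but 6.2.1.3 does not make the monitor's agreement a condition.
- **Delays of more than 6 weeks for reasons other than treatment-related toxicity need joint review by monitor and investigator (6.2.1.3).** This covers long CNS-related holds. It leaves shorter ones, which are the restarts most likely to come before the CNS lesions have been treated.
- **The size of the problem is not measured.** Counting clauses and scheduled doses does not measure harm, and the documents give no frequency. That is correct.

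**Conclusion.** The concern holds. For the same event, 6.2.1.3 lacks two of the three restart conditions in 6.6: sponsor agreement and adequately treated CNS lesions. The steroid limit is not in conflict.

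The subjects affected are those with CNS metastases arising or worsening on study who have not already been stopped under another rule. Their number cannot be derived from the documents. The textual difference is certain; how often it would lead to a restart that 6.6 forbids is unknown, and the medical monitor's role makes it less likely. No endpoint, sample size or analysis is affected. The change should be made because it concerns subject safety and the stricter rule is already in the protocol.

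**What to change.** Replace the resumption sentence in 6.2.1.3 with: *Resumption is permitted only under the conditions in Section 6.6.* Restart would then require adequately treated lesions, a steroid dose no higher than physiologic replacement, and agreement of investigator and sponsor.

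This is in line with comparable decisions elsewhere. Section 6.9 already requires investigator and sponsor to agree on re-exposure after unexpected surgery. Section 6.4.3 goes further for rechallenge after potential hepatotoxicity, which "should be discussed and agreed upon unanimously by the subject or legally acceptable representative, investigator, and Amgen medical monitor"; that is a three-party rule, so the parallel lies in requiring agreement and not in the exact parties.

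The cost is one sentence and some loss of investigator discretion.

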6.9 Excluded Treatments, Medical Devices, and/or Procedures During Study Period

Subjects must not use any of the following therapies during screening or treatment period, unless indicated otherwise:

- other investigational agents or procedures
- concurrent experimental or approved anticancer therapies other than study drug and radiation therapy required for palliation.

In addition, the following are not permitted during the treatment period:

- Immunosuppressive agents with the exception of treatment for adverse events
- If the subject requires corticosteroid dosing for related toxicities, talimogene laherparepvec treatment must be withheld until the corticosteroid dose has decreased to doses acceptable for maintenance physiologic replacement
- Subjects who are receiving talimogene laherparepvec may not receive systemic antiherpetic drugs (eg, acyclovir, valacyclovir, famciclovir), but may receive a topically administered antiherpetic drug more than 20 cm from a talimogene laherparepvec injection site with the exception of treatment for adverse events.
- Childhood vaccinations that contain live attenuated virus

If a subject undergoes any unexpected surgery during the course of the study, all study treatments must be withheld and the investigator or designee should notify the sponsor's medical monitor as soon as possible. Re-exposure to talimogene laherparepvec may occur only if the investigator and sponsor agree that the subject safety will not be compromised.

Subjects in the safety follow-up period who have not demonstrated confirmed disease progression, rapid clinical deterioration, **clinical progression**, or intolerance to talimogene laherparepvec may not receive any experimental or approved antitumor therapies unless the sponsor's medical monitor is consulted and approved.

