7.2.3.2 Long-term Follow-up

After the safety follow-up visit all subjects will enter the long-term follow-up. Subjects will be asked to come for a clinic visit or contacted by telephone to assess survival and initiation of additional anticancer therapy.

Contact for all subjects will be attempted every 12 weeks (\pm 28 days) following the safety follow-up visit until death, subject or legally acceptable representative withdraws full consent/assent, or up to approximately 24 months after the last subject is enrolled in the study, whichever comes first. During long-term follow-up concomitant medications recording is to be restricted to anticancer therapy and safety reporting will be limited to talimogene laherparepvec related adverse events.

For subjects who discontinued treatment for any reason other than confirmed PD, every effort should be made to perform radiographic scan for tumor assessments every 12 weeks until documentation of confirmed PD per modified irRC-RECIST, start of new anticancer therapy, or end of study, whichever occurs first.

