8.3 Reasons for Removal From Treatment or Study

8.3.1 Reasons for Removal From Treatment

Reasons for removal from protocol-required investigational product(s) or procedural assessments include any of the following:

- subject (or a legally acceptable representative) request
- safety concern (eg, due to an adverse event, ineligibility determined, protocol deviation, non-compliance, requirement for alternative therapy, pregnancy, other protocol-specified criteria)

- death
- lost to follow-up
- decision by sponsor (other than subject request, safety concern, lost to follow-up)
- disease progression (confirmed PD per modified irRC-RECIST or clinical progression)
- other protocol-specified criteria ([Section 6.2.1.2.3](#))

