### Best overall response (BOR) per Modified irRC-RECIST

Best overall response (BOR) of complete response (CR), partial response (PR), stable disease (SD), progressive disease (PD) or un-evaluable (UE) will be derived based on

investigator assessment using modified irRC-RECIST as defined in protocol Appendix D. Any baseline tumor markers above the ULN must normalize for an overall visit response of CR.

Overall visit response assessments occurring after the start of the first subsequent anticancer therapy, including complete or partial removal/reduction of any target lesion, will not be included. Consecutive confirmation of CR, PR, and PD is required where the second overall response must be at least 28 days from the first, the only exception being when the investigator reports that an initial PD cannot be confirmed due to rapid clinical deterioration. The following will be considered a confirmed PR: CR followed by PR or PR followed by CR.

BOR is defined as the best visit response in the following order: CR, PR, SD, PD, or UE (see [Table 3](#)). BOR is defined as SD if the best overall visit response is an unconfirmed CR or PR, and UE if it is either SD earlier than 49 days after the date of first dosing or an unconfirmed PD when confirmation of PD is required (ie, initial PD without rapid clinical deterioration).

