**Duration of response (DOR) per Modified irRC-RECIST**

Duration of response (DOR) is defined as the time from the date of an initial response that is subsequently confirmed to the earlier of PD (see definition of BOR per Modified irRC-RECIST) or death. Subjects who have not ended their response at the time of analysis will be censored at their last evaluable tumor assessment.

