**Progression-free survival (PFS) per Modified irRC-RECIST**

Progression-free survival (PFS) per Modified irRC-RECIST is defined as the interval from first dose to the earlier of PD per Modified irRC-RECIST or death from any cause; otherwise, PFS is censored at the last evaluable tumor assessment. The initial date of PD will be the PFS date when it is consecutively confirmed.

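### Clinical progression ends treatment but is not an event for PFS, TTP or DOR, so a child stopped for it with no PD scan is censored or counted only at death

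*Protocol*

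**What the plan says.** **Stopping treatment.** Protocol 6.2.1.3 lists among the criteria for permanent discontinuation: "Confirmed PD occurs as defined per modified irRC-RECIST or clinical progression per the investigator". Protocol 8.3.1 repeats this as one reason for removal: "disease progression (confirmed PD per modified irRC-RECIST or clinical progression".

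**Other therapy.** Protocol 6.9 says that children in safety follow-up "may not receive any experimental or approved antitumor therapies" without the medical monitor's approval, but it exempts those who have shown clinical progression.

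**Scans after stopping.** Table 3 schedules a radiographic scan at the safety follow-up visit, about 30 (+7) days after the last dose. For children who stopped for a reason other than confirmed PD, Protocol 7.2.3.2 asks sites to try to scan every 12 weeks "until documentation of confirmed PD per modified irRC-RECIST, start of new anticancer therapy, or end of study, whichever occurs first". For deterioration without objective PD, Appendix D asks that the reason be recorded and that objective progression still be sought.

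**Endpoints (SAP 6).** PFS runs to the "earlier of PD per Modified irRC-RECIST or death from any cause; otherwise, PFS is censored at the last evaluable tumor assessment". TTP ends only at PD per modified irRC-RECIST, with the same censoring. DOR runs from the first confirmed response "to the earlier of PD (see definition of BOR per Modified irRC-RECIST) or death", otherwise censored at the last evaluable assessment. PD is a tumor-burden criterion: at least 20% and 5 mm above nadir.

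**The concern.** The protocol treats clinical progression as progression when it decides about treatment. The SAP does not count it when it measures time to progression. No rule in either document says how PFS, TTP or DOR handles it, and no sensitivity analysis covers it.

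This matters in three ways. For TTP, the children censored are those whose investigator has just judged them to be progressing, so the censoring is informative. For PFS and DOR, two children with the same scans and the same clinical progression date get different outcomes according to later vital status. And the direction favours the product, with no control arm to offset it. In a group of 18, one child is 1/18 = 5.6% of the sample (1/24 = 4.2% in a group of 24), so a few such children can move the curve visibly.

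**Working it through.** The plan states no figure for this point, so the check has two parts: a trace of the rules, and a size under assumed inputs.

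**1. Trace, with assumed dates.** Last evaluable scan stable on day 50; treatment stopped for clinical progression on day 70; no later scan.

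| Status at cutoff | PFS | TTP |
|---|---|---|
| Died day 180 | event, day 180 | censored, day 50 |
| Alive | censored, day 50 | censored, day 50 |

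The progression on day 70 is never an event. DOR in a responder follows the PFS pattern.

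**2. Does another rule close the gap?** The SAP's only clinical route is its category for PD with rapid clinical deterioration (BOR definition and Table 3). It waives the confirmatory scan for a PD already seen. It does not turn deterioration without a PD scan into PD.

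**3. Size for PFS.** Assumptions, none from the documents:
- progression exponential with median 3 months, rate λ = ln 2/3 = 0.231 per month
- survival after progression exponential with median m, rate μ = ln 2/m
- a share f of children progress clinically only and have no later scan
- all are followed beyond 6 months.

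Only the clinical-only children differ between the two rules. As written they leave PFS at death (time D); with clinical progression as an event they leave at progression (time P). So

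gap at 6 months = f × [Pr(D > 6) − Pr(P > 6)],

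where Pr(P > 6) = 2^(−6/3) = 0.25 and Pr(D > 6) = (λe^(−6μ) − μe^(−6λ))/(λ − μ).

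- m = 9: μ = 0.0770, e^(−6μ) = 0.630. Pr(D > 6) = (0.231 × 0.630 − 0.0770 × 0.25)/0.154 = 0.82. The bracket is 0.57, so the gap is 5.7 points at f = 10%, 11.4 at 20% and 22.8 at 40%.
- m = 2: μ = 0.347, e^(−6μ) = 0.125. Pr(D > 6) = (0.231 × 0.125 − 0.347 × 0.25)/(0.231 − 0.347) = 0.50. The bracket is 0.25, so the gap is 2.5 points at 10% and 10 at 40%.

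Simulation with scans at weeks 8, 16 and 28, then every 12 weeks, agrees. At a 40% share, 6-month PFS is:

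| m (months) | As written | Clinical progression as event | Gap (points) |
|---|---|---|---|
| 9 | 56.8% | 34.6% | 22.2 |
| 6 | 54.0% | 34.4% | 19.6 |
| 3 | 46.7% | 32.9% | 13.8 |
| 2 | 42.1% | 31.9% | 10.2 |

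At a 20% share and m = 9 it is 49.1% against 37.7%, a gap of 11.4.

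**4. Allowing for the safety follow-up scan.** Suppose it documents PD in half of these children (assumption). The gap at m = 9 falls from 11 to about 6 points (20% share) and from 22 to about 12 (40% share). At m = 2 and a 10% share, half of 2.5 is 1.25. The late date of the scan adds at most 0.05 × (2^(−5/3) − 0.25) = 0.05 × 0.065, or 0.3 points. The low end is therefore about 2 points.

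**5. Size for TTP.** Simulation with scans every 8 weeks, the same 3-month median, survival after progression of 2, 4 or 8 months, and no later scan. The 6-month progression-free proportion as written, against clinical progression as an event:
- 10% share: 41.1/36.0/33.4% against 36.0/31.7/29.7%, gaps of 5.1, 4.3 and 3.7 points
- 25% share: 46.6/42.1/39.7% against 33.8/30.9/29.0%, gaps of 12.8, 11.2 and 10.7 points.

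No size is offered for DOR, which concerns responders only.

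**The case against.** **The endpoint is objective by design.** PFS, TTP and DOR are labelled as per modified irRC-RECIST. Protocol 6.2.1.1 explains that tumors may grow, or new ones appear, before benefit. Clinical progression is undefined and is judged by investigators in an open-label trial. This stands, and it is why the main definition should not change. It does not explain why the effect of the choice should go unreported.

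**The missing progressions may be found anyway.** The safety follow-up scan is scheduled, not best-effort, and the 12-weekly scans may add more. This also stands in part: step 4 shows that it could halve the gap. New therapy may start before that scan, however, and a PD found later is dated at the scan.

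**The stakes are limited.** These are secondary, descriptive endpoints with no test attached. This stands.

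**Two stronger readings are tempting.** A reader might infer that once new therapy starts a PD can be neither seen nor counted. The documents do not go that far. Protocol 7.2.3.2 ends only the 12-weekly scans. The SAP sentence beginning "Overall visit response assessments occurring after the start of the first subsequent anticancer" belongs to the BOR definition; it reaches DOR by cross-reference, and PFS and TTP only by inference.

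A reader might also infer that the main PFS and DOR should be censored at the last assessment before new therapy. That is itself informative censoring and discards real deaths. At a 40% share it moves 6-month PFS from 56.8% to 55.9% (m = 9), 54.0% to 55.2% (m = 6), 46.7% to 53.2% (m = 3) and 42.1% to 51.7% (m = 2). It removes almost nothing when survival after progression is long and enlarges the error when it is short.

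**Conclusion.** The gap is real. For children stopped for clinical progression with no PD on any scan, the plan censors TTP at the last evaluable scan, and PFS and DOR either there or not at all until death. The estimates look too favourable as a result.

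Under the stated assumptions the overstatement of 6-month PFS is about 2 to 22 points (22.2 simulated, 22.8 by formula at the top). The low end is a 10% share, 2 months' survival after progression and half the cases caught at safety follow-up. The high end is a 40% share, 9 months' survival and none caught. The documents give neither the share nor the survival, so no figure inside that range can be called the expected one. The direction was the same in every scenario with a non-zero share.

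The documents do not support calling the main PFS definition wrong, and DLT incidence and OS are unaffected. This is a modest but worthwhile improvement to the SAP.

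**What to change.** In SAP 6 and 10.5.1:

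1. Keep PD per modified irRC-RECIST as the definition in the main analysis, with no added censoring at new therapy.
2. Add a pre-specified supplementary Kaplan-Meier analysis of PFS, TTP and DOR in which permanent discontinuation for clinical progression without documented PD is an event on the discontinuation date.
3. Report the number of such children beside the main result.
4. Protocol 8.3.1 groups confirmed PD and clinical progression as one removal reason. Identify these children, therefore, as those discontinued for disease progression with no PD per modified irRC-RECIST on or before that date.

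The cost is SAP wording and one extra set of tables. SAP 10.2 already provides for reporting reasons for ending treatment, and the visit responses needed for item 4 are collected. The drawback is reliance on open-label investigator judgment, which is why the analysis is supplementary. No treatment rule changes.
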